5.6.4 Loss to follow-up

For subjects whose status is unclear because they fail to appear for study visits without stating an intention to discontinue or withdraw, the investigator must show "due diligence" by documenting in the source documents steps taken to contact the subject, e.g. dates of telephone calls, registered letters, etc. A patient cannot be considered as lost to follow-up until the time point of his/her scheduled end of study visit has passed.

5.6.5 Early study termination by the sponsor

Novartis may terminate the trial for reasons related to the benefit risk assessment of treatment for participants in the study, or for regulatory or medical reasons (including slow enrollment). In the event that the study is terminated early, the Institutional Review Boards (IRBs)/Ethics Committees (ECs) will be informed and will be asked to approve the process to prematurely withdraw the participants. In general, the participant should be seen as soon as possible and assessed as a prematurely withdrawn participant from the study. The withdrawal process may include additional procedures to be followed, in order to ensure that adequate consideration is given to the protection of the participant's interests.

6 Visit schedule and assessments

[Table 6-1](#) lists all of the assessments and indicates with an "X" or "S" when the visits are performed.

Patients must be seen for all visits on the designated date or as close to it as possible. (Suggested window is +/- 3 days with the exception of V199 and V201 which must be performed no later than 13-week after the Baseline visit.)

For V199 and V201, the scheduled dates should be strictly adhered to avoid treatment exposure of more than 13 weeks after baseline visit.

The scheduled visit date should be calculated based on V101 (BL) for all visits from V101 (week 0) till V201 (week 13).

Missed or rescheduled visits should not lead to automatic discontinuation. Patients who prematurely discontinue the study treatment for any reason should be scheduled for a visit as soon as possible, at which time all of the assessments listed for the Treatment Discontinuation visit (TD) will be performed. At this visit, all dispensed investigational product should be reconciled and the adverse event and concomitant medications reconciled on the CRF. If patients then agree to continue in the study (for further safety and efficacy data collection), subsequent visits will then be according to the Abbreviated schedule of assessments for patients with study treatment discontinuation as outlined in [Table 6-2](#). Patients following the Abbreviated schedule of assessments must continue to adhere to the protocol requirements for changes to concomitant medications for neuropathic pain, rescue medication and prohibited medications.

Patients will be contacted for safety evaluations during the 30 days following the last administration of study treatment.

[figure not shown]
[figure not shown]

Table 6-1 Assessment schedule

Epoch	Screening	Treatment									Treatment withdrawal
		101	102	103	104	105	106	107	199	TD visit	
Visit	1	101	102	103	104	105	106	107	199		201
Week	-5 to -1	0 (BL)	1	2	4	6	8	10	12	TD visit	13
Day	-35 to -7	1	8	15	29	43	57	71	85		92
Informed consent	X										
Inclusion/Exclusion criteria	X										
Demography	X										
Disease & Medical History	X										
Smoking, Alcohol, Liver History	X										
Surgical and medical procedures/Concomitant Medications/Rescue Medications	X	X	X	X	X	X	X	X	X	X	X
Complete Physical exam	S	S							S	S	S
Brief Physical exam			S	S	S	S	S	S			
Vital signs	X	X	X	X	X	X	X	X	X	X	X
Height	X										
Weight	X	X							X	X	
Urine drug screen	X				X						
Serum pregnancy test ^{1,2}		X							X	X	
Urine pregnancy test	X				X		X				X
Hematology/Blood chemistry	X	X	X	X	X	X	X	X	X	X	X
Urinalysis ³	X	X			X		X		X	X	X
12-lead ECG ^{5,6}	X	X			X		X		X	X	X
Contact IRT	X	X	X	X	X	X	X	X	X	X	X
Dispense study medication		S	S	S	S	S	S	S	S ⁷		

Epoch	Screening	Treatment									Treatment withdrawal
Visit	1	101	102	103	104	105	106	107	199	TD visit	201
Week	-5 to -1	0 (BL)	1	2	4	6	8	10	12		13
Day	-35 to -7	1	8	15	29	43	57	71	85		92
Dosage Administration Record		X	X	X	X	X	X	X	X		X
Treatment Compliance			S	S	S	S	S	S	S		S
Adverse Events/SAEs	X	X	X	X	X	X	X	X	X	X	X
Dispense ePRO eDiary device	S										
Complete pain diary daily (NRS)	X	X	X	X	X	X	X	X	X	X	X
Record VRS pain intensity		X									
Check electronic tablet for eligibility		S									
BPI-SF		X			X		X		X	X	
PGIC									X	X	
NPSI		X			X		X		X	X	X
ISI		X							X	X	
Pharmacokinetics		X ¹⁰					X ^{9,10}		X ^{9,10}		
Screening disposition	X										
Treatment epoch disposition									X	X	
Treatment withdrawal epoch disposition											X
TD = Study Treatment Discontinuation visit X = assessment to be recorded on clinical data base; S = assessment to be recorded on source documentation only ¹ Collected as part of the blood chemistry. ² Required for all pre-menopausal women who are not surgically sterile. ³ Urine dipstick to be performed at the site. If abnormalities are present, urine sample should be sent to the central laboratory for microscopy analysis.											

Epoch	Screening	Treatment									Treatment withdrawal
Visit	1	101	102	103	104	105	106	107	199		201
Week	-5 to -1	0 (BL)	1	2	4	6	8	10	12	TD visit	13
Day	-35 to -7	1	8	15	29	43	57	71	85		92

⁵Triplicate ECG and PK sample should also be collected if abnormal ECG result (QTcF>500 ms).

⁶Should blood sampling procedures, ECG and vital signs assessments be required at the same visit, the blood sampling procedures should be started after completion of the ECG collection and hemodynamic assessments as shown in the following sequence: 10 min resting period & pre-dose single ECG → Vital signs → Pre-dose PK & lab samples → Study drug administration.

⁷Drug dispensation only for patients continuing into Treatment withdrawal epoch. Patients will take their last dose of "Treatment" study medication from their old bottle at the site visit in the morning, and will take their first dose of "Treatment withdrawal" study medication from their new bottle that evening.

⁹PK samples for all patients should be collected according to the schedule detailed in [Table 17-1](#). Patients should be instructed not to take their morning dose of study medication prior to arriving at the site and completing the necessary assessments. PK sample should also be collected if abnormal ECG result (QTcF>500 ms).

¹⁰Additional PK sample collected for patients taking pregabalin or gabapentin according to the schedule detailed in [Table 17-2](#). Patients should be instructed not to take their morning dose of pregabalin/gabapentin prior to arriving at the site and completing the necessary assessments. Patients should bring their pregabalin/gabapentin (if applicable) with them to the study visits where PK is collected so it may be administered after the PK assessment, as required.

[figure not shown]

[figure not shown]
Table 6-2 Abbreviated schedule of assessments for patients with data collected after study treatment discontinuation

Epoch	Treatment						
Visit ^{1,2}	102	103	104	105	106	107	199
Week	1	2	4	6	8	10	12
Day	8	15	29	43	57	71	85
Complete Physical exam							S
Brief Physical exam	S	S	S	S	S	S	
Surgical and medical procedures/Concomitant Medications	X	X	X	X	X	X	X
Adverse Events/SAEs	X	X	X	X	X	X	X
Complete pain diary daily (NRS)	X	X	X	X	X	X	X
BPI-SF, NPSI			X		X		X
PGIC							X
Treatment epoch disposition							X

X = assessment to be recorded on clinical data base; S = assessment to be recorded on source documentation only

¹The abbreviated schedule should be adopted from the visit following the study treatment discontinuation. For example, if a patient discontinues study drug at Week 4, the patient should be scheduled for the TD visit (Table 6-1) as soon as possible and then follow the abbreviated schedule for Week 6 and subsequent visits (Table 6-2). At premature withdrawal from the study, or at completion of the study, the End of Study visit assessments (V199) should be performed instead of the next scheduled visit.

²Patients following the Abbreviated schedule of assessments must continue to adhere to the protocol requirements for changes to concomitant medications for neuropathic pain, rescue medication and prohibited medications.

6.1 Information to be collected on screening failures

All patients who have signed informed consent but not entered into the double-blind Treatment epoch will have the Screening phase disposition, demographics, inclusion/exclusion, and serious adverse event (SAE) data collected. Adverse events that are not SAEs will be followed by the investigator and collected only in the source data.

6.2 Patient demographics/other baseline characteristics

Patient demographic and baseline characteristic data to be collected on all patients include: date of birth, age, sex, race, ethnicity, relevant medical history/current medical condition present before signing informed consent. Where possible, diagnoses, and not symptoms, will be recorded.

Investigators will have the discretion to record abnormal test findings on the medical history CRF whenever in their judgment, the test abnormality occurred prior to the informed consent signature.

6.3 Treatment exposure and compliance

Compliance will be assessed by the investigator and/or study personnel at each visit using pill counts and information provided by the patient. This information should be captured in the source document at each visit. All study treatment dispensed and returned must be recorded in the Drug Accountability Log.

Investigator should also check the electronic patient diaries and remind the patient of the importance of daily completion.

[figure not shown]
Protocol Deviations should be recorded for patients with an overall compliance of less than 80% or patients with more than 3 full consecutive days of missed doses (more than 6 consecutive doses).

6.4 Efficacy

Assessments are to be collected as specified in [Table 6-1](#). At study visits, all questionnaires should be completed first before any other study assessments are done.

A detailed training manual relating to the administrative procedures of the questionnaires will be provided to the sites.

All questionnaires will be completed in the language most familiar to the respondent, at the scheduled study visit prior to the patient seeing the investigator for any clinical assessment or evaluation. The patient should be given sufficient instruction, space, time and privacy to complete the questionnaire. The study coordinator should check the responses to the questionnaire for completeness and encourage the patient to complete any missing responses.

All patients will complete the Patient Reported Outcome (PRO) questions via a handheld electronic device or an electronic tablet. Detailed training on use of the device should be provided and recorded in the patient's source document. Attempts should be made to collect responses to all PROs for all patients, including from those who prematurely discontinue prior to the study evaluation completion visit, however, if patients refuse to complete PROs, this should be documented in study source records.

Designated Investigator site staff will review eDiary compliance with the patient at each visit. Completed questionnaires will be reviewed and examined by the investigator, before the clinical examination, for responses that may indicate potential adverse events (AEs) or serious adverse events (SAEs), and the review should be documented in the patient's source document accordingly. If AEs or SAEs are confirmed, then the physician must record the events as per instructions given in [Section 7.1](#) and [Section 7.2](#) of the protocol.

6.4.1 11-point Numeric Rating Scale (NRS)

The Numeric Rating Scale (NRS) is an 11-point scale for patient self-reporting of pain.

24-hour Average Pain Score

The 24-hour average pain score will be assessed using the 11-point numeric rating scale (NRS) scale ranging from zero to ten. Patients will evaluate their average pain during the past 24 hours in the evening prior to sleep by touching the appropriate corresponding number between zero ("no pain") and ten ("pain as bad as you can imagine") on the eDiary device.

The 24-hour average pain score should be completed daily for seven consecutive days prior to randomization and then every day through the end of the study. Patients will be allowed to record their pain scores up to 1 day in the past. Any entries >1 day old will not be allowed and will be considered missing data.

Please note that patients will be required to bring their eDiary device in to the clinic for every study visit, and should return the eDiary device at the end of study.

24-hour Worst Pain Score

[figure not shown]
The 24-hour worst pain score will also be assessed using the 11-point NRS scale ranging from zero to ten. Patients will rate their worst pain during the past 24 hours in the evening prior to sleep by touching the appropriate corresponding number between 0 ("no pain") and ten ("pain as bad as you can imagine") on the eDiary device.

The 24-hour worst pain score should be completed daily for seven consecutive days prior to randomization and then every day through the end of the study. Patients will be allowed to record their pain scores up to 1 day in the past. Any entries >1 day old will not be allowed and will be considered missing data.

Please note that patients will be required to bring their eDiary device in to the clinic for every study visit, and should return the eDiary device at the end of study.

6.4.2 Verbal Rating Scale (VRS) pain intensity

The Verbal Rating Scale (VRS) is a questionnaire administered by the clinician to capture the patient's level of pain.

At Baseline, the designated investigator site staff will capture pain intensity information from each patient using the 4-point categorical VRS. The patient will be asked “What is your pain level at this time?” and the response will be recorded as 0 = none, 1 = mild, 2 = moderate, and 3 = severe. This will be recorded in the electronic tablet at the site.

6.4.3 Brief Pain Inventory- Short Form (BPI-SF)

The Brief Pain Inventory-Short Form (BPI-SF) is a validated, self-administered questionnaire that assesses pain severity and its impact on daily functions.

Patients will be asked to complete the 7-item pain interference scale which assesses the degree to which pain interferes with walking and other physical activity, work, mood, relations with others and sleep using a zero to ten numeric rating scale, with zero being "does not interfere" and ten being "completely interferes."

The 7-item pain interference scale of the BPI-SF will be completed by patients using the electronic tablet at the site at the specified visits.

6.4.4 Patient Global Impression of Change (PGIC)

The Patient Global Impression of Change (PGIC) is a patient-reported instrument that measures change in overall status on a scale ranging from one ("very much improved") to seven ("very much worse").

The PGIC is based on the validated Clinical Global Impression of Change scale.

The PGIC will be completed by patients using the electronic tablet at the site at the specified visit.

6.4.5 Neuropathic Pain Symptom Inventory (NPSI)

The Neuropathic Pain Symptom Inventory (NPSI) is a 12 item patient reported outcome measure that contains 10 descriptors representing 5 dimensions of pain (burning pain, deep/pressing pain, paroxysmal pain, evoked pain and paraesthesia/dysesthesia) and 2 temporal items designed to assess pain duration and the number of pain paroxysms.

[figure not shown]
The NPSI will be completed by patients using the electronic tablet at the site at the specified visits.

[figure not shown]
6.4.6 Insomnia Severity Index (ISI)

The Insomnia Severity Index (ISI) is a validated seven-item patient questionnaire used to quantify perceived insomnia severity.

Patients will be asked to complete the ISI using five-point Likert-style scale as a measure of perceived sleep difficulties. Scores can range from zero to 28, with a cut-off score of eight suggesting the presence of sub-threshold insomnia. The questionnaire assesses the severity of insomnia, satisfaction with current sleep pattern, sleep interference, "noticeability" of sleeping problem to others and concern about sleeping problems.

The ISI will be completed by patients using the electronic tablet at the site at the specified visits.

6.4.10 Appropriateness of efficacy assessments

Efficacy assessments used for evaluation of pain relief (NRS) are standard recommended primary outcome measures for neuropathic pain clinical trials, also supported by Food and Drug Administration (FDA) and European Medicines Agency (EMA) guidelines. As chronic pain interferes with daily activities, quality of life, additional patient reported outcome measures (PROs) of physical functioning, [REDACTED] tools are recommended for assessing the patient's perception of the impact of disease and treatment on daily life physical, psychological and social functioning and well-being. Therefore BPI-SF, [REDACTED] [REDACTED] are included.

Co-morbid anxiety and depression are common in chronic pain patients. Mood changes, anxiety and sleep disturbance may change pain perception and might affect efficacy assessments. Furthermore pharmacodynamic effects of EMA401 may influence these comorbidities. [REDACTED] [REDACTED] ISI will be used to assess impact on the comorbid conditions. Global Impression of Change reported by the patient is a useful supportive indicator of the overall perceived benefit of treatment in chronic pain trials.

NPSI is a multidimensional tool to evaluate treatment response on sensory and affective qualities of pain.

6.5 Safety

6.5.1 Physical examination

[figure not shown]
A complete physical examination will include the examination of general appearance, skin, neck (including thyroid), eyes, ears, nose, throat, lungs, heart, abdomen, back, lymph nodes, extremities, vascular and neurological. If indicated based on medical history and/or symptoms, rectal, external genitalia, breast, and pelvic exams will be performed.

A brief physical exam, as per local practice, will include the examination of general appearance and will be at all visits, except where a complete physical examination is required (see above).

Information for all physical examinations must be included in the source documentation at the study site. Clinically relevant findings that are present prior to signing informed consent must be included in the Medical History part of the CRF. Significant findings made after signing informed consent which meet the definition of an Adverse Event must be recorded on the Adverse Event section of the CRF.

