3.3.4 Clinical Safety

Eight studies in healthy subjects and two in patients have been completed for EMA401. Three hundred seventy three unique subjects (250 healthy subjects, 92 patients with PHN, and 31 patients with Chemotherapy Induced Neuropathic Pain (CINP)) have received EMA401, and 183 subjects (92 healthy subjects and 91 patients with PHN) have received placebo in the clinical program till date. Maximum doses tested were up to 2000 mg in single ascending dose (SAD), 800 mg b.i.d. (1600 mg/d) for 7 days in multiple ascending dose (MAD), and 100 mg b.i.d. (200 mg/d) in Phase 2 for 28 days.

No deaths or SAEs have been attributed to EMA401.

Study EMA401-008 determined maximum tolerated doses (MTDs) for EMA401 in healthy volunteers. Gastrointestinal AEs (particularly nausea and diarrhea) were the most significant dose-related AEs in subjects who received EMA401. All reported TEAEs were mild to moderate in severity in both single and multiple ascending cohorts. There was an apparent dose-related trend in gastrointestinal events in both the SAD and MAD components with highest incidence in single dose of 2000 mg or 800 mg b.i.d. multiple dose cohorts. As a result, these two dose levels have been determined to be the single and short-term repeat maximum tolerated doses (MTDs) for EMA401, respectively.

In PHN patients (Study EMA401-003), EMA401 demonstrated an acceptable safety profile and was well-tolerated. Overall, 32 patients reported 56 treatment emergent adverse events (TEAEs) in the EMA401 group compared to 29 patients reporting 45 TEAEs in the placebo group. TEAEs of headache, allergic dermatitis and pharyngitis were observed more frequently with EMA401 treatment compared to placebo. All reported TEAEs events were mild to moderate in severity. Patients were allowed to use concomitant medications for PHN, including pregabalin and gabapentin, and other comorbid conditions (e.g. insomnia, depression). No safety concerns were identified with use of EMA401 and concomitant medications over 4 weeks.

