9.5.2 Safety variables

Safety analyses will be conducted using the safety (SAF) dataset. Patients will be grouped by the actual treatment received.

The assessment of safety will be primarily based on the frequency of adverse events (including death and non-fatal serious adverse events). Additional safety assessments include laboratory tests, physical examination (including examination of skin), vital sign measures and ECG evaluations. Clinically significant findings in these additional safety assessments will be reported as adverse events and analyzed as such. In addition all safety assessments will be summarized or listed as appropriate. The analyses of additional safety assessments will be defined in the statistical analysis plan.

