9.5.2.2 Potential risks and Expected events

Allergic dermatitis, elevation in hepatic enzymes and neutropenia are the potential risks related to EMA401. Dizziness, headache, nausea, pre syncope and upper respiratory tract infections are the expected events related to EMA401. The search criterion for each of these risks and events will be defined based on MedDRA. The incidence of potential risks and expected events will be summarized. The detailed analysis of potential risks and expected events will be specified in the statistical analysis plan.

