2.8.1 Adverse events (AEs)

Treatment-emergent adverse events (TEAEs) are defined as any adverse events that develops after initiation of study treatment or any event already present that worsens following exposure to the study treatment.

If an adverse event starts at the date of week 12 visit it should be allocated to the treatment epoch and not to the treatment withdrawal epoch.

TEAEs will be summarized (number of cases as a percentage of number at risk) by treatment group separately for treatment epoch and treatment withdrawal epoch. Adverse events reported 21 days after end of study date in the scope of USM will not be included in the summary tables, but will be listed. Number and percentage of patients with TEAE will be summarized by primary system organ class and preferred term for each treatment group during the double blind Treatment epoch and during the double-blind Treatment withdrawal epoch. Severity will be classified as "mild", "moderate" and "severe". Serious TEAEs, TEAEs by maximum severity and TEAEs leading to premature discontinuation from study drug will be presented in a similar format as adverse events. Additionally, a listing of patients with TEAE will be presented. Drug abuse-related adverse events (identified using a pre-specified search criterion) will be summarized during the double-blind Treatment epoch. To assess the potential for withdrawal

effect, drug abuse-related adverse events will be summarized for the double-blind Treatment withdrawal epoch.

The following additional analysis will be performed.

- Analysis of TEAES with onset date before 25-Feb-2019

For rash adverse events, following details will be listed:

- Laterality and location of rash
- Did the subject start any new topical non-pharmaceutical products within the last 14 days prior to the start of rash?
- Topical Non-pharmaceutical Products related to the event of rash including soap, detergent, perfume, cologne and lotion.
- Were there any additional contributing factors that may have led to the rash?
- Did the dermatologist agree with the event?
- Additional investigation performed to diagnose that event: yes, no

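### Between baseline and Week 12, no scheduled examination has to include the skin of a patient who stays on drug, although allergic dermatitis is a named risk of EMA401

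*Protocol*

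**What the plan says.** Protocol 6.5.1 defines two examinations. The first covers skin: "A complete physical examination will include the examination of general appearance, skin, neck (including thyroid", followed by a list of other systems. The second is minimal: "A brief physical exam, as per local practice, will include the examination of general appearance". It is done at every visit apart from those that call for the complete one. Skin is not mentioned in it.

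Table 6-1 assigns the complete examination to screening (V1), baseline (V101), Week 12 (V199), the treatment discontinuation (TD) visit and Week 13 (V201). V102 to V107 (Weeks 1, 2, 4, 6, 8 and 10) have the brief one.

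The plan treats skin reactions as important:
- Protocol 9.5.2.2: "Allergic dermatitis, elevation in hepatic enzymes and neutropenia are the potential risks related to EMA401".
- Protocol 3.3.4, on the earlier PHN study: "TEAEs of headache, allergic dermatitis and pharyngitis were observed more frequently with EMA401 treatment compared to placebo".
- Protocol 3.6 and 8.4 make allergic dermatitis a case of interest for the DMC, and 3.6 has such cases reported to it in real time.
- Protocol 5.6.2 makes skin rash a reason to interrupt study drug and obtain a dermatologist's view, with an exception for clearly unrelated causes.
- Protocol 9.5.2 lists among the safety assessments "physical examination (including examination of skin), vital sign measures and ECG evaluations".

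Protocol 7.1 has AEs sought by non-directive questioning at each visit. It also accepts events that patients volunteer or that an examination reveals. SAP 2.8.1 summarizes TEAEs "by treatment group separately for treatment epoch and treatment withdrawal epoch". SAP 2.8.4.3 keeps examination findings, including skin, in source documents only.

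**The concern.** Of the three risks the protocol names, two have an objective test at every treatment visit and the third does not. For patients who stay on drug, nothing in the schedule obliges anyone to look at the skin between the baseline and Week 12 visits. The documents give no reason for the difference.

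Three things depend on rash being noticed:
- **Incidence and onset.** A mild or covered rash that the patient does not mention may be missed. It may also be first recorded at Week 12 or the TD visit, with an unreliable onset date.
- **The interruption rule.** It can act only on a rash that someone has seen or reported.
- **The DMC review that gates the 300 mg b.i.d. arm.** Under Protocol 8.4 and 9.7 it follows at least 8 weeks of exposure, which is earlier than the first required post-baseline skin check.

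**Working it through.** The plan states no examination or ascertainment rate, so there is no figure to reproduce. The check is a count from Table 6-1, with study days from the same table.

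| Visit | Day | Examination | Skin required | Hematology/chemistry | AE enquiry |
|---|---|---|---|---|---|
| V101 | 1 | complete | yes | yes | yes |
| V102 | 8 | brief | no | yes | yes |
| V103 | 15 | brief | no | yes | yes |
| V104 | 29 | brief | no | yes | yes |
| V105 | 43 | brief | no | yes | yes |
| V106 | 57 | brief | no | yes | yes |
| V107 | 71 | brief | no | yes | yes |
| V199 | 85 | complete | yes | yes | yes |
| V201 | 92 | complete | yes | yes | yes |

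**Required skin checks on treatment.** The post-baseline treatment visits are V102 to V107 and V199, so 6 + 1 = 7. Skin is required at 1 of 7. Laboratory tests that cover the other two named risks are done at 7 of 7.

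**Longest gap between required skin checks.** 85 − 1 = 84 days for a patient who stays on drug. A patient who stops has a complete examination at the TD visit, so stopping at week *w* gives a gap of about *w* weeks (4 at Week 4, 8 at Week 8).

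**DMC review before the 300 mg b.i.d. arm.** A patient still on drug at Week 8 (V106) has had five post-baseline visits (V102 to V106). That means five sets of laboratory tests and no required skin check. Patients already past Week 12 at the review would have had one.

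**Comparison with the withdrawal week.** Rates are per week, using epochs of 12 weeks and 1 week:
- Required skin checks: 1/12 = 0.083 against 1/1 = 1.0, a ratio of 12. If the baseline check is counted as well, 2/12 = 0.167 and the ratio is 6.
- Scheduled AE enquiries: 7/12 = 0.583 against 1/1 = 1.0, a ratio of 1.7.

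**Effect on the comparison with placebo.** The schedule is the same in every arm. Let a rash be detected with probability *s* in each arm, with true risks *p1* on EMA401 and *p0* on placebo. The observed risks are *s·p1* and *s·p0*. Their ratio stays *p1/p0*, and their difference shrinks to *s(p1 − p0)*. The loss is therefore in counts and in the absolute difference, and neither arm is favored. The documents give no value for *s*.

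**After naming skin in the brief examination.** Required checks rise from 1 to 7 of 7. The longest gap falls to 14 days (for example Day 15 to Day 29). The ratio to the withdrawal week falls from 12 to 1/0.583 = 1.7.

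**The case against.** The strongest reply is that rash is recorded as an AE and AEs are sought at every visit. A clinician also sees the patient at V102 to V107. The wording on local practice sets a minimum and does not rule out a skin check. Patients who stop drug have a complete examination, and a suspected allergic dermatitis has its own work-up. Much of this stands, and it defeats three stronger readings that a reader might infer:

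- *Rash ascertainment is 12 times sparser on treatment than in withdrawal.* The 12 is the ratio of scheduled skin-naming examinations only, which is 84 days over 7. For scheduled AE enquiry the ratio is 1.7, before volunteered reports.
- *Rash in Weeks 1 to 10 is found only if the patient reports it.* Examination findings also count under Protocol 7.1, and a site may look at the skin by local practice.
- *Rash rates by epoch are distorted.* SAP 2.8.1 assigns an event starting on the Week 12 visit date to the treatment epoch, so a rash dated late to that visit still counts there. The epochs are summarized separately, and no comparison of rash between them is planned.

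Nor does Protocol 9.5.2 contradict the schedule. It lists skin examination as an assessment without promising it at every visit.

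The reply does not close the gap. Non-directive questioning means nobody has to ask about rash, and whether anyone looks depends on the site. A rash neither mentioned nor seen leaves no trace in the database.

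On cost, a change to 6.5.1 is a protocol amendment needing ethics approval across about 100 to 120 planned centers. The SAP also records that the trial ended early with 129 of 360 patients randomized and that the 300 mg b.i.d. arm was not initiated. The point about the DMC review therefore concerns the plan as written.

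**Conclusion.** The point holds as a gap in the examination schedule. For a patient who stays on drug, a skin check is required at 1 of 7 post-baseline treatment visits and at none from Day 2 to Day 84. The other two named risks are tested at all 7. The consequence is lower sensitivity to mild or unreported rash and less accurate onset dates. It also means less objective information on this risk for a DMC review held after 8 weeks of exposure.

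The number of events affected cannot be estimated, because the documents give neither allergic dermatitis counts nor a detection rate. The finding does not bias EMA401 against placebo within an epoch, provided detection does not depend on arm, which the common schedule and the blinding support. It also rests on reading the brief examination as requiring only what it names. Sites whose local practice includes skin would not have the gap. It is a worthwhile, inexpensive improvement and does not threaten the primary analysis.

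**What to change.** In Protocol 6.5.1, name skin beside general appearance as an item of the brief physical examination at V102 to V107. Findings would be recorded as AEs, as already planned, with the rash details listed in SAP 2.8.1. No visit, form or analysis has to be added.

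The cost is one phrase, carried by an amendment, and a few minutes at visits already scheduled with the same staff. The downside is slightly more minor skin findings reported as AEs.

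If data collection is closed, no examination can be added. The study report should then state that skin examination was not required at Weeks 1 to 10, and that rash incidence and onset dates in that period rest on AE questioning, volunteered reports and local practice.
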